### **5.12. Safety Analyses**

#### **5.12.1. Adverse Events**

TEAEs are defined as the reported AEs that first occurred or worsened during the postbaseline phase compared with baseline phase. For each TEAE, the severity level of the event (mild, moderate, or severe) will be determined by patient or physician opinion. The MedDRA Lowest Level Term (LLT) will be used in the treatment-emergent computation. For each LLT, the maximum severity at baseline will be used as the baseline severity. If the maximum severity during postbaseline is greater than the maximum baseline severity, the event is considered as treatment-emergent for the specific postbaseline period.

For each patient and TEAE, the maximum severity for the MedDRA level being displayed (PT, High Level Term, or SOC) is the maximum postbaseline severity observed from all associated LLTs mapping to that MedDRA level.

For events that are sex-specific, the denominator and computation of the percentage will include only patients from the specific sex.

The safety and tolerability of treatment will be assessed by summarizing (using standard descriptive statistics) and listed on the SAF. The following parameters will be reported:

- TEAEs
- SAEs
- AEs leading to discontinuation
- Potential hypersensitivity events
- AEs related to injection site reactions
- Vital signs
- Physical and neurological examinations
- ECGs
- Laboratory measurements
- CBB

Additional analysis will be performed as required.

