9.2. Adverse Events

A clinical trial AE is any untoward medical event associated with the use of a drug or drug delivery system in humans, whether or not it is considered related to that drug or drug delivery system.

Investigators are responsible for monitoring the safety of patients who have entered this study and for alerting Lilly or its designee to any event that seems unusual, even if this event may be considered an unanticipated benefit to the patient.

The investigator is responsible for the appropriate medical care of patients during the study.

Investigators must document their review of each laboratory safety report and ECG.

The investigator remains responsible for following, through an appropriate health care option, AEs that are serious or otherwise medically important, considered related to the investigational

product or the study, or that caused the patient to discontinue the investigational product before completing the study. The patient should be followed until the event resolves, stabilizes with appropriate diagnostic evaluation, or is reasonably explained. The frequency of follow-up evaluations of the AE is left to the discretion of the investigator.

Lack of drug effect is not an AE in clinical studies, because the purpose of the clinical study is to establish treatment effect. However, any worsening of the primary study condition should be recorded as an AE.

After the ICF is signed, study site personnel will record via EDC the occurrence and nature of each patient's pre-existing conditions, including clinically significant signs and symptoms of the disease under treatment in the study. In addition, site personnel will record via eCRF any change in the condition(s) and any new conditions as AEs. Investigators should record their assessment of the potential relatedness of each AE to protocol procedure or investigational product via EDC.

The investigator will interpret and document whether or not an AE has a reasonable possibility of being related to study treatment, study device, or a study procedure, taking into account the disease, concomitant treatment, and pathologies.

A "reasonable possibility" means that there potentially is a cause and effect relationship between the investigational product, study device, and/or study procedure and the AE.

The investigator will use AE follow-up forms to record additional details regarding AEs related to injection sites and hypersensitivity events.

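### SAP 5.12.1 does not restrict displayed TEAE severity to the treatment-emergent LLTs, so a mild TEAE can be shown at a higher grade (minor wording gap)

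*SAP*

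**What the plan says.** SAP 5.12.1 starts from the usual definition: "TEAEs are defined as the reported AEs that first occurred or worsened during the postbaseline phase compared with baseline phase". It then sets the level of the test, "The MedDRA Lowest Level Term (LLT) will be used in the treatment-emergent computation", and the reference, "For each LLT, the maximum severity at baseline will be used as the baseline severity". The test is a strict inequality: "If the maximum severity during postbaseline is greater than the maximum baseline severity, the event is considered as treatment-emergent for the specific postbaseline period". An LLT whose grade is unchanged or lower after dosing is therefore not treatment-emergent.

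The next paragraph covers display. Its subject is "For each patient and TEAE, the maximum severity for the MedDRA level being displayed (PT, High Level Term, or SOC" (the bracket closes there), and that severity "is the maximum postbaseline severity observed from all associated LLTs mapping to that MedDRA level".

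The protocol has no competing rule. Section 10.3.4 lists TEAEs among the safety summaries, and Appendix 1 defines the term; neither says how severity is derived at a displayed level. Protocol 9.2 governs which records exist. After consent, sites record "pre-existing conditions, including clinically significant signs and symptoms of the disease under treatment in the study". They then report changes in those conditions, and new conditions, as AEs. Worsening of the study disease is also to be reported as an AE.

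**The concern.** The two steps have different scope. The first sorts LLTs into treatment-emergent and not. The second takes a maximum over every LLT under the displayed level, without using that sorting. An event that did not emerge on treatment can then set the grade of one that did. In one variant the event that sets the grade actually improved after dosing, which conflicts with the SAP's own definition of a TEAE.

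TEAEs are an endpoint for a secondary objective. SAP 5.11.4 drops the secondary and exploratory efficacy analyses because enrollment was insufficient, while 5.12.1 keeps the safety summaries, so safety forms a larger share of what will be reported. All patients have migraine, and pain of moderate or severe intensity is one of its features in Protocol Appendix 6, so high-grade background records are plausible. Background severity carried into a TEAE table in both arms would tend to blur a real severity difference.

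**Working it through.** The documents give no figure on this point, so the check is to write the rule out and apply it to constructed records.

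**Inputs.** From SAP 5.12.1: grades mild, moderate, severe; emergence test per LLT; severity rule per displayed level. From Protocol 9.2: which conditions receive a postbaseline AE record.

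**Notation.** For LLT *i* under one PT, HLT or SOC, let b_i and p_i be the maximum baseline and postbaseline severity, coded 0 none, 1 mild, 2 moderate, 3 severe.

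- Emergent: p_i > b_i.
- Literal rule: if any LLT is emergent, displayed severity = max of p_i over all LLTs under the level.
- Restricted rule: displayed severity = max of p_i over emergent LLTs only.

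**Constructed cases** (baseline to postbaseline):

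| New LLT | Pre-existing LLT | Literal | Restricted |
|---|---|---|---|
| 0 to 1 | 3 to 3, with a postbaseline record | severe | mild |
| 0 to 1 | 3 to 2 (improved) | moderate | mild |
| none | 3 to 3 | no TEAE | no TEAE |
| 0 to 1 | 2 to 3 (grade rose) | severe | severe |
| 0 to 1 | 3, no postbaseline record | mild | mild |

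**How often the rules can differ, as patterns.** Each LLT has 4 × 4 = 16 baseline-postbaseline pairs; 6 are emergent and 10 are not. Two LLTs give 16 × 16 = 256 patterns, of which 256 − 10 × 10 = 156 contain a TEAE. The rules differ when the non-emergent LLT has the higher postbaseline grade:

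- emergent LLT at mild (b = 0, 1 way), other LLT 2 to 2, 3 to 2 or 3 to 3: 1 × 3 = 3;
- emergent LLT at moderate (b = 0 or 1, 2 ways), other LLT 3 to 3: 2 × 1 = 2.

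That is 5, doubled because either LLT can be the emergent one: 10 of 156. This counts patterns and is not an expected frequency. In all 10 the literal rule gives the higher grade, never the lower.

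**Does the protocol generate such records?** Take a patient whose migraine is severe at baseline and becomes more frequent after dosing. Protocol 9.2 has this reported as an AE. If it is coded to the same LLT as the baseline condition and graded severe, then p = b = 3. It cannot exceed the top grade, so it fails the emergence test. If the patient also has a new mild dizziness, which Protocol 7.6.1 lists as an infusion-reaction symptom, and both code to one SOC, the first row of the table applies. The shared LLT and SOC coding are assumptions, since the documents give no coding. A pre-existing condition that recurs or improves leads to the same place if the change is reported.

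**The case against.** The strongest defence is grammatical. The sentence is about each patient and TEAE, so the associated LLTs could be taken to be those belonging to that TEAE, and the paragraph before has just defined emergence per LLT. The SAP never says that non-emergent terms are included; a reader might infer a deliberate choice, and the text does not support that. What the text shows is a missing restriction. The defence does not remove the gap, however: the opening words fix which patients and levels are shown, while the words that select the LLTs are *all* and the mapping to the displayed level. A programmer following them would pool non-emergent LLTs.

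A second objection stands in full. A reader might infer that any stable severe condition, such as unchanged migraine, inflates TEAE severity. Protocol 9.2 asks for AE records of changes and new conditions only, and neither document says that an unchanged condition is carried forward with a postbaseline severity. Without such a record the two rules agree (last row of the table). Likewise, a condition whose grade rises is itself treatment-emergent and is correctly counted.

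Third, the consequences are limited, and this also stands. The endpoint is TEAEs and SAEs, with no severity test or decision rule attached. SAP 5.12.1 names no by-severity table; one is implied by the reference to a displayed level. Event listings remain available for review.

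**Conclusion.** The gap is real on the literal wording, and its priority is minor. It can raise the displayed severity of a TEAE at PT, HLT or SOC level when a non-emergent LLT under the same level has a higher postbaseline grade. It is most plausible at SOC level. It cannot create a TEAE or alter TEAE or SAE counts. It reaches only patients who already have a TEAE at that level and also have such a record.

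The size cannot be calculated. A reader might try to derive a count from the planned enrollment (about 60 randomized 1:1, so about 30 per arm), but the documents give neither a TEAE rate nor a rate of co-occurring non-emergent records, and SAP 5.11.4 reports that enrollment was insufficient.

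The conclusion assumes that baseline conditions carry a severity grade, as the SAP's comparison presupposes, and that the AE program follows the sentence as written. If the program already filters on treatment emergence, only the wording needs correcting.

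**What to change.** In the severity sentence of SAP 5.12.1, replace *all associated LLTs* with *the treatment-emergent LLTs*, so that the maximum runs only over LLTs under the displayed level that met the emergence test. Apply or confirm the same filter in the AE program. With the filter in place, an unchanged or improved condition cannot affect displayed severity whether or not it has a postbaseline record, so no carry-forward convention is needed for this purpose. The cost is one phrase and one filter; no endpoint, visit or data collection changes, and output that is already filtered stays as it is.

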## **5.13. Pharmacokinetic/Pharmacodynamic Analyses**

Pharmacokinetic and PK/pharmacodynamic analyses are the responsibility of the PK scientist. Details will be provided in the PK/pharmacodynamic analysis plan.

## **5.14. Evaluation of Immunogenicity**

The data for the evaluation of immunogenicity is available in the SDTMs for any analyses to be performed if needed.

## **5.15. Other Analyses**

### **5.15.1. *Health Outcome Analyses***

The data for health outcome analyses is available in the SDTMs for any analyses to be performed if needed.

### **5.15.2. *Migraine Specific Quality of Life (MSQ)***

The data for MSQ is available in the SDTMs for any analyses to be performed if needed.

### **5.15.3. *Headache Impact Test (HIT-6)***

The data for HIT-6 is available in the SDTMs for any analyses to be performed if needed.

### **5.15.4. *Analysis of Columbia-Suicide Severity Rating Scale (C-SSRS) Data***

The data for C-SSRS is available in the SDTMs for any analyses to be performed if needed.

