9.2.1. Adverse Event Monitoring with a Systematic Questionnaire

Nonleading AE collection should occur prior to the collection of the C-SSRS.

If a suicide-related event is discovered during the C-SSRS but was not captured during the nonleading AE collection, sites should not change the AE form.

If an AE is serious or leads to discontinuation, it needs to be included on the AE form and the process for reporting SAEs is followed.

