9.2.2. Serious Adverse Events

An SAE is any AE from this study that results in one of the following:

- death
- initial or prolonged inpatient hospitalization
- a life-threatening experience (that is, immediate risk of dying)

- persistent or significant disability/incapacity
- congenital anomaly/birth defect
- important medical events that may not be immediately life-threatening or result in death or hospitalization but may jeopardize the patient or may require intervention to prevent one of the other outcomes listed in the definition above.

The study site personnel must alert the Lilly, or its designee, of any SAE as soon as practically possible.

Additionally, study site personnel must alert Lilly, or its designee, of any SAE within 24 hours of Investigator awareness of the event via a Sponsor-approved method. If alerts are issued via telephone, they are to be immediately followed with official notification on study-specific SAE forms. This 24-hour notification requirement refers to the initial SAE information and all follow-up SAE information.

Although all AEs are recorded in the case report form or EDC after signing informed consent, SAE reporting to the Sponsor begins after the patient has signed informed consent and has received the study drug. However, if an SAE occurs after signing informed consent, but prior to receiving the study drug, AND is considered Reasonably Possibly Related to a study procedure then it MUST be reported.

Investigators are not obligated to actively seek AEs or SAEs in patients once they have discontinued from and/or completed the study (the patient disposition EDC has been completed). However, if the Investigator learns of any SAE, including a death, at any time after a patient has been discharged from the study, and he/she considers the event reasonably possibly related to the study treatment or study participation, the Investigator must promptly notify Lilly.

Pregnancy (maternal or paternal exposure to the study drug) does not meet the definition of an adverse event. However, to fulfill regulatory requirements any pregnancy should be reported following the SAE process to collect data on the outcome for both mother and fetus.

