10.3.4. Safety Analyses

The safety and tolerability of treatment will be assessed by summarizing the following:

- TEAEs
- SAEs
- AEs leading to discontinuation

- Potential hypersensitivity events
- AEs related to injection site reactions
- Vital signs
- Physical and neurological examinations
- ECGs
- Laboratory measurements
- CBB

The parameters will be listed, and summarized using standard descriptive statistics. Additional analysis will be performed as required.

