10.3.7.2. Analysis of C-SSRS Data

Suicide-related thoughts and behaviors occurring during treatment will be summarized based on responses to the C-SSRS consistent with the C-SSRS Scoring and Data Analysis Guide.

Additional details will be provided in the SAP.

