#### **5.11.4. Secondary and Exploratory Efficacy Endpoints**

Due to insufficient enrollment only the primary endpoint is to be evaluated. The data for all secondary and exploratory endpoints is available in the SDTMs for any analyses to be performed if needed.

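### The SAP plans no C-SSRS output although the protocol commits to one, so non-serious, non-discontinuing events found only by C-SSRS reach no planned by-arm report

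*SAP*

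**What the plan says.** Protocol 10.3.7.2 is unconditional: "Suicide-related thoughts and behaviors occurring during treatment will be summarized based on responses to the C-SSRS". It ties the summary to the C-SSRS Scoring and Data Analysis Guide and refers the reader to the SAP for details.

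SAP 5.15.4, the section under that heading, consists of one sentence: "The data for C-SSRS is available in the SDTMs for any analyses to be performed if needed". It names no table, listing, analysis set, period or method, and the section is not redacted. The guide remains in the SAP's reference list, but no SAP section applies it.

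The SAP states a reason for cutting analyses in one place, 5.11.4: "Due to insufficient enrollment only the primary endpoint is to be evaluated". That sentence stands under the heading for secondary and exploratory efficacy endpoints.

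Protocol 9.2.1 governs how C-SSRS findings reach the AE form. If a suicide-related event comes to light in the C-SSRS but "was not captured during the nonleading AE collection, sites should not change the AE form". The exception follows: "If an AE is serious or leads to discontinuation, it needs to be included on the AE form".

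**The concern.** A reader following the SAP exactly would produce no C-SSRS output, although the protocol says there will be one. For many measures a dropped summary would be partly covered by the AE tables. Here it is not, because the protocol deliberately keeps some C-SSRS findings off the AE form, and the C-SSRS summary is where those findings would have been reported by arm.

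At stake is the comparative reporting of suicidal ideation and behavior after a single dose of a new antibody. The conditional wording also leaves open whether suicidality results will be shown at all, and that decision could then be taken after the data are known.

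**Working it through.** No figure in the plan needs reproducing and no formula applies. The check traces one event through the documents and then looks for any other planned output that would carry it.

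**Step 1. Route of an event found by C-SSRS but missed at nonleading AE collection.**

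| Type of event | On the AE form (Protocol 9.2.1)? | Planned SAP output |
|---|---|---|
| Serious | Yes | SAE and AE tables, registry summary |
| Leads to discontinuation | Yes | AEs leading to discontinuation |
| Neither | No | None |

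The third row follows because SAP 5.12.1 builds TEAEs from reported AEs. The serious category is broad: Protocol 9.2.2 includes "important medical events that may not be immediately life-threatening or result in death or hospitalization but may jeopardize the patient". The third row is therefore likely to hold mainly non-serious ideation.

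**Step 2. Other SAP outputs that might carry it.**

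- SAP 5.12.1 states: "The safety and tolerability of treatment will be assessed by summarizing (using standard descriptive statistics) and listed on the SAF". Its list has 10 items, and C-SSRS is not one of them. Protocol 10.3.4 has the same 10 items and says of them: "The parameters will be listed, and summarized using standard descriptive statistics". It omits C-SSRS too, so the commitment rests on Protocol 10.3.7.2 alone.
- SAP 5.17 plans no exploratory analyses.
- SAP 5.18 is a registry summary of AEs.
- SAP 5.19 has 5 reports: exposure, disposition, demographics, deaths, and discontinuations due to AE.

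Planned outputs that would show C-SSRS results: 0.

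**Step 3. Is C-SSRS different from the other measures treated this way?** Outside efficacy, six SAP sections carry the same conditional sentence (5.14 and 5.15.1 to 5.15.5):

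- Immunogenicity (5.14): 1 section. Protocol 10.3.6 makes its tabulation optional.
- Health outcomes, MSQ and HIT-6 (5.15.1 to 5.15.3): 3 sections. Protocol 10.3.7.1 makes a firm commitment here as well, but these are not safety measures.
- Cognition (5.15.5): 1 section. The cognitive battery is still in the SAP 5.12.1 list.
- C-SSRS (5.15.4): 1 section, with a firm commitment and no other output.

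1 + 3 + 1 + 1 = 6. C-SSRS is the only safety measure of the six with a firm protocol commitment and no other SAP output.

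**Step 4. Period and baseline.** The protocol's schedule collects the C-SSRS since-last-visit form at Visits 2 to 11 and at early discontinuation. Visits 4 to 11 are the 8 scheduled visits after the dosing visit. SAP Table 5.1 ends the treatment period at Visit 5, so a summary limited to it covers 2 of the 8 (Visits 4 and 5) and leaves 6 (Visits 6 to 11). The general baseline rule in Table 5.1 takes the last assessment on or before dosing. For C-SSRS that would normally be the Visit 3 form, which sets aside the screening form at Visit 1 and the form at Visit 2.

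**The case against.** The strongest reply is procedural. Protocol 10.3.1 requires an amendment only when a principal feature changes. Other changes to the analysis methods, with their justification, are to be described in the clinical study report. A descriptive C-SSRS summary is probably not a principal feature, and the study report is not among the documents. This stands in part: the omission may be formally curable, and it would be wrong to say that it needs an amendment. But the route requires a justification, the SAP offers none for C-SSRS, and a justification would still leave the third row of the trace without an output.

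A second reply is that the SAP reduces its scope throughout, so C-SSRS was not singled out. That is correct. MSQ and HIT-6 lost firm commitments in the same way. Low enrollment may be the common cause, but the SAP states it for efficacy only, and a descriptive count with a listing does not depend on power.

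A third reply is that SAP 5.12.1 allows further analyses as required. It does, but it plans none and does not name C-SSRS.

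Four stronger readings are tempting, and the documents do not support them:

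- *Suicidal events in general go unreported.* Events captured at nonleading collection, serious events and events leading to discontinuation all reach the AE form.
- *Patients are not watched.* Protocol 9.4.6.5 and 8.1.1 cover monitoring and the response to C-SSRS findings. The gap is in reporting.
- *The summary was dropped because of what the data showed.* SAP 5.11.2 describes observed diary compliance, so that text was written with some data in hand. Nothing shows that C-SSRS results by arm had been seen, and the same sentence appears in six sections.
- *The protocol promised a summary of follow-up events.* Its commitment is to events during treatment, and it does not say whether follow-up visits count.

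**Conclusion.** The point holds and should be fixed before reporting. Followed as written, the SAP omits a safety summary to which the protocol commits, gives no reason, and leaves one class of event without any planned by-arm output: found only by C-SSRS, not serious, and not leading to discontinuation.

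Its size is one firm commitment against zero outputs. The documents give no rate for such events, so the number affected could be none or several. TEAE and SAE reporting, patient monitoring and the primary efficacy inference do not change.

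The conclusion assumes that sites apply Protocol 9.2.1 as written and that no separate reporting document, unseen here, specifies a C-SSRS output.

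**What to change.** In SAP 5.15.4, replace the conditional sentence with two outputs on the safety analysis set:

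1. A descriptive table by arm giving the number and percentage of patients with suicidal ideation, and with suicidal behavior, during the treatment phase. This delivers what Protocol 10.3.7.2 commits to.
2. A patient listing of C-SSRS findings from all post-dose visits (Visits 4 to 11 and early discontinuation), so that events in follow-up are reported as well.

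Take the baseline or pre-treatment reference from the C-SSRS Scoring and Data Analysis Guide named in the protocol, and say that the general rule in SAP Table 5.1 does not apply to this measure. The guide's own rule could not be checked from these documents.

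The cost is a few sentences in the SAP, one table and one listing from data already collected. It needs no new data and no protocol amendment.
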